3.4.3.2 Time to First Migraine after Dosing

The analysis of the time to the first migraine after dosing endpoint will be based upon Kaplan-Meier method. The 25th percentile, 50th percentile (median), and 75th percentile, and their corresponding 95% confidence intervals will be reported for each treatment group. The percent of subjects who are migraine free at Days 1, 2, 3, 4, 5 and 6 and Weeks 1, 4, 8, 12 and the associated confidence intervals will be summarized for each treatment group. A subject will

be censored for the eDiary analysis at the time of their last data entry. A Kaplan-Meier plot for time to first migraine will be presented for weeks 1-12.

3.4.4 Remaining Headache and Migraine Secondary Endpoints

The following summarizations will be produced for headache episodes, migraine attacks, headache and migraine hours, headaches and migraines with severe intensity and headaches and migraines with acute medication usage. A summary table including confidence intervals for the treatment difference for the 4, 12, and 24-week time intervals will be produced.

Missing data rule for both Missing Data Rules provided in Section 2.7.2 will be utilized. For severe intensity and acute medication usage endpoints, the missing data rule will be applied to the nominator and denominator separately before calculating the percent.

3.4.5 Tertiary and Exploratory Headache and Migraine Endpoints

The following summarizations will be produced for headache and migraine characteristics, the average length of a headache episode and migraine attack, and headaches and migraines summarized by **type** of acute medication usage. A summary table including confidence intervals for the treatment difference for the 4-week time intervals will be produced.

Missing data rule for Missing Data Rule 1 provided in Section 2.7.2 will be utilized for the exploratory analyses.

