2.2 Clinical Trial Endpoints

The efficacy, safety, pharmacokinetic and immunogenicity of ALD403 will be assessed using the following endpoints. Greater detail concerning these endpoints can be found in Section 2.2.2.

Primary Efficacy Endpoint

• Change in frequency of migraine days (Weeks 1-12)

Key Secondary Efficacy Endpoints

- 75% migraine responder rate (Weeks 1-4)
- 75% migraine responder rate (Weeks 1-12)
- 50% migraine responder rate (Weeks 1-12)
- Percentage of subjects with a migraine on the day after dosing

Other Secondary Efficacy Endpoints

- Change in acute migraine medication days (Weeks 1-12)
- Headaches/Migraines with acute medication usage
- 100% migraine responder rates (Weeks 1-12)
- Short-Form Health Survey (SF-36 v 2.0)
- Health-Related Quality of Life (EQ-5D-5L)
- Allodynia Symptom Checklist-12 (ASC-12)
- Brush (dynamic mechanical) Allodynia
- Migraine responder rates for time periods other than Weeks 1-12
- Change in frequency of migraine days between baseline and time periods other than Weeks 1-12
- Headache responder rates
- Change in the frequency of headache days
- Percent change in headache/migraine days
- Time to first migraine after dosing
- Headache/Migraine hours
- Headache/migraines with severe intensity

Tertiary Endpoints

• Headache episodes/migraine attacks

Exploratory Endpoints

- Headache/Migraine characteristics
- Headaches/Migraines with type of acute medication usage
- Headache episode/Migraine attack average length

Safety Endpoints

- Adverse events (AEs) and serious adverse events (SAEs)
- Changes in clinical laboratory assessments
- Vital Signs
- ECGs
- Suicidal ideation and behavior as measured by the Columbia-Suicide Severity Rating Scale (C-SSRS)

Pharmacokinetic Endpoints

• Free ALD403 plasma concentrations

Immunogenicity Endpoints

- Development of specific anti-ALD403 antibodies
- Characterization of specific anti-ALD403 antibodies for neutralizing activity

2.2.1 eDiary

Subjects will complete a daily headache eDiary from the time of screening to Week 48. The diary is to be completed each trial day whether or not the subject had a headache. These daily entries record if the subject took acute migraine medication on that day.

The eDiary data from the 28 days following screening visit will be used to determine eligibility criteria, and the baseline migraine and headache results.

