2.7.2 Handling of Dropouts or Missing Data

Summary statistics will be reported based upon observed data except for the diary data, which will utilize the imputation outlined below. Additionally, if the start date of an AE or concomitant medication is incomplete or missing, it will be assumed to have occurred on or after the intake of trial medication, except if an incomplete date (e.g., month and year) clearly indicates that the event started prior to treatment.

Subjects who do not complete the eDiary daily will have missing data. It is expected that most missing diary data will be sporadic.

Missing Headache End Date and Time

If the end date and time for a headache recorded in the eDiary is missing the headache end date will be set to the earlier of 23:59 on the day before the next reported headache or 23:59 on the last entry reported into the diary (i.e. the last evening report or if no evening report was completed after the start of the headache 23:59 on the day the headache started). Headaches that are not reported as stopped by the subject are missing the answers to the questions that allow for the determination of whether the headache was a migraine or not. In this population most headaches are migraines. Hence, these headaches with missing 'end' information will be classified as migraines.

Missing Data Rule 1

If the eDiary has been completed at least 21 days in a 28 day interval, then a normalization procedure will be used. The results will be normalized to 28 days by multiplying the observed results by the inverse of the completion rate (e.g. if a subject does not complete the eDiary on 5 days they will have completed the diary on 82% of the days and the normalized results will be the observed results times 1.22).

Missing Data Rule 2

If the eDiary has been completed on less than 21 days in the 28 day interval then the results for the 28 day interval will be a weighted function of the observed data for the current four week interval and the results from the previous interval. The weights will be proportional to how many days the diary was completed and will provide greater weight for higher completion rates. Specifically, the results will be derived as

$$28 (W X_c + (1 - W) X_p),$$

where W is the number of days the diary was completed/20, X_c is the available average daily results for the current interval and X_p are the average imputed daily results for the previous interval.

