Unless it is stated otherwise all primary and secondary analyses will use both Missing Data Rules 1 and 2, as appropriate. For the exploratory analyses, only Missing Data Rule 1 will be used and the denominators for will reflect the number of subjects who completed the eDiary 21 or more days in the 28 day interval.

Sensitivity Rule

The primary endpoint and key secondary endpoints will also be analyzed using a modification to Missing Date Rule 2 to better understand the robustness of the selected algorithm. The analysis replaces X_p with X_b , where X_b are the baseline average daily results, if the subject withdrew from the study due to an adverse event, study burden, lack of efficacy or worsening of study indication or if the subject died.

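### As written, Missing Data Rule 1 scales average attack length by 28/days completed, although a mean per attack does not grow with the number of days observed

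*SAP*

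**What the plan says.** SAP 2.2 lists "Headache episode/Migraine attack average length" under Exploratory Endpoints. SAP 2.2.2 (Average Migraine / Headache Length) defines it as the mean of the attack durations within a four-week interval and gives subjects with no attacks a duration of zero.

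SAP 2.7.2 sets out Missing Data Rule 1. Its condition is: "If the eDiary has been completed at least 21 days in a 28 day interval, then a normalization procedure will be used". Its operation is: "The results will be normalized to 28 days by multiplying the observed results by the inverse of the completion rate". The worked example, for five missed days, gives "82% of the days and the normalized results will be the observed results times 1.22".

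The same section assigns the rule: "For the exploratory analyses, only Missing Data Rule 1 will be used". It adds that denominators will reflect subjects with 21 or more completed days. SAP 3.4.5 names "the average length of a headache episode and migraine attack" among the results it covers, plans a table with confidence intervals for the treatment difference by four-week interval, and repeats the assignment: "Missing data rule for Missing Data Rule 1 provided in Section 2.7.2 will be utilized for the exploratory analyses".

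SAP 3.4.4 has a safeguard for ratios: "the missing data rule will be applied to the nominator and denominator separately before calculating the percent". It names only the severe-intensity and acute-medication-usage endpoints. SAP 3.4.5 has no matching instruction.

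**The concern.** Rule 1 extrapolates from observed days to 28 days. Migraine days, attacks and hours accrue with observation time, so this is sensible for them. Average length is total duration divided by number of attacks. Both parts accrue, and their ratio does not. A subject who fills in 21 days instead of 28 does not have shorter attacks that need scaling up.

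The compliance definition in SAP 3.3.7 points the same way. A day is missing only if the subject neither used the diary nor had a headache. On that definition no recorded attack lies on a missing day, and the mean already uses every recorded duration.

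At stake is how the average-length table can be read. If the rule is programmed literally, the means and the treatment differences with their intervals combine attack duration with diary compliance, and a reader cannot separate the two.

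**Working it through.** **Inputs.** From SAP 2.7.2: factor = 1/(completion rate) = 28/d, where d is days completed; lower limit d = 21. From SAP 2.2.2: average length = mean duration per attack. Assumed, because the documents do not give them: a 12-hour attack, four attacks in the interval, and mean completion by arm.

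**1. The SAP's own figure.** Five missed days leave d = 23. 23/28 = 0.8214, which is 82%. 28/23 = 1.2174, which rounds to 1.22. The example is reproduced, so 28/d is the intended factor.

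**2. Factor over the range where Rule 1 applies.**

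| d | 28/d | Inflation of a mean |
|---|---|---|
| 28 | 1.000 | 0% |
| 27 | 1.037 | 3.7% |
| 26 | 1.077 | 7.7% |
| 25 | 1.120 | 12.0% |
| 24 | 1.167 | 16.7% |
| 23 | 1.217 | 21.7% |
| 22 | 1.273 | 27.3% |
| 21 | 1.333 | 33.3% |

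Below 21 days the subject leaves the exploratory denominator, so 1.333 is the ceiling for one subject in one interval.

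**3. Literal rule against the SAP 3.4.4 approach.** Take four attacks of 12 hours (48 hours in total) and d = 21.
- Literal: (48/4) × 28/21 = 12 × 1.333 = 16.0 hours.
- Each part scaled, then divided: (48 × 1.333)/(4 × 1.333) = 64/5.333 = 12.0 hours.

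In the second form the factor is (28/d)/(28/d) = 1.00 for every d from 21 to 28.

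**4. Equal completion in both arms.** If every subject completes d days and the true difference in mean length is D, the reported difference is (28/d) × D, for example 1.077 × D at d = 26. If D = 0, it stays 0.

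**5. Unequal completion with no true difference.** Approximate each arm's average factor by 28/(mean days). The ratio of the reported means is then the inverse ratio of mean days:
- no gap: 26.5/26.5 = 1.000, so 0%;
- half a day, 26.5 versus 26.0: 26.5/26.0 = 1.019, about 2%;
- one day, 26.5 versus 25.5: 26.5/25.5 = 1.039, about 4%;
- two days, 26.5 versus 24.5: 26.5/24.5 = 1.082, about 8%.

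The arm with lower completion appears to have longer attacks. For the one-day gap and a 12-hour attack: 12 × 28/26.5 = 12.68 hours and 12 × 28/25.5 = 13.18 hours, a spurious difference of about 0.5 hour. Subjects with no attacks stay at zero under either rule.

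**The case against.** The best defence is that normalising to 28 days has meaning only for quantities that accrue over days, so for average length Rule 1 can serve only as the 21-day inclusion threshold. SAP 3.4.4 shows that the sponsor knew a ratio should not be scaled directly, and a sensible programmer might leave the mean alone. That may well be the intention, but the text does not say it. SAP 2.7.2 states the use of Rule 1 and the 21-day denominator as two separate things. Where the SAP wants the bare threshold, it writes it that way: SAP 3.3.4 limits the diary medication summaries to subjects with at least 21 of 28 days and does not invoke Rule 1.

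Other parts of the defence stand and limit the point. The endpoint is exploratory and descriptive (SAP 2.5) and lies outside the testing sequence (SAP 2.7.5). SAP 2.7.2 expects most missing diary data to be sporadic, and nothing in the documents suggests that compliance will differ between blinded arms.

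Two stronger readings are tempting and are not supported:
- **Percentages above 100%.** A reader might infer that a by-type medication result, such as 90% of migraines treated with a given type, would be reported as 0.90 × 1.333 = 120%. SAP 3.4.5 does not say that these results are percentages of migraines. A count per 28 days fits equally well, and Rule 1 is correct for a count. It is also correct for the by-type measure that SAP 2.2.2 does define, the percentage of days per 28 days: with k medication days, k/28 × 28/d = k/d.
- **Attacks that seem to lengthen on treatment.** Eligibility requires at least 25 of 28 diary days at baseline, while later intervals may fall to 21. One could therefore infer a spurious rise of 1.333/1.120 = 1.19, or up to 1.333 from a full baseline diary. SAP 3.4.5 plans no change-from-baseline analysis of length. SAP Table 3 does define a baseline interval for all diary endpoints, so the comparison could be made by eye, but it is not a planned estimate.

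**Conclusion.** The point holds for average headache episode/migraine attack length. SAP 2.7.2 and 3.4.5 together apply a 28/d multiplier to a mean per attack, and the ratio safeguard in SAP 3.4.4 does not reach it. This is a stated rule that gives a wrong result for this endpoint, and not merely a missing detail.

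The 33% is a maximum for one subject in one interval, reached at exactly 21 completed days. It is not an estimate of bias in a group mean. That bias cannot be sized from the documents, and the figure of about 4% between arms rests entirely on the assumed one-day gap in mean completion. With equal completion, no difference is created where none exists, but a true difference is rescaled. The consequence is confined to an exploratory descriptive table, and the importance is accordingly low.

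**What to change.** In SAP 2.7.2 and 3.4.5:
- State that Rule 1 scaling applies only to counts and sums.
- Report average length unscaled, among subjects with at least 21 of 28 diary days in the interval.
- Keep the SAP 2.2.2 convention of zero for subjects with no attacks. Redefining the endpoint only as total hours over number of attacks would give 0/0 for them, so leaving the mean unscaled is simpler.
- If any exploratory medication-type or headache-characteristic result is shown as a percentage of headaches or migraines, apply the rule to numerator and denominator separately, as in SAP 3.4.4.

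The cost is a short addition to the SAP text and a small programming change. No extra data are needed.

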3.4.6 Other Secondary Efficacy Analyses

The secondary endpoints will be summarized with descriptive statistics by time point. These summary measures will be based upon the observed results and where appropriate the change from baseline results. The denominator for percentages will be the total number of assessments collected at each visit.

3.4.6.1 Short-Form Health Survey (SF-36 v 2.0)

The actual scores and change from baseline in each of the eight sections will be summarized using the Full Analysis Population at each scheduled visit by treatment group using descriptive

31

statistics. Scoring software utilizing the 2009 norm-based scoring algorithm will be used to calculate the actual score for each of the eight sections.

3.4.6.2 EQ-5D-5L

The change from baseline will be summarized separately for each EQ-5D-5L item using the Full Analysis Population at each scheduled visit by treatment group. A shift from baseline to each scheduled visit by treatment group will be tabulated for each item.

3.4.6.3 Allodynia Symptom Checklist-12 (ASC-12)

The ASC-12 total score and change from baseline will be summarized using the Full Analysis Population at each scheduled visit by treatment group using descriptive statistics. In addition, allodynia severity will be summarized using frequency counts for each scheduled visit.

3.4.6.4 Brush (dynamic mechanical) Allodynia

Brush allodynia will be summarized as a continuous measure and binary (does or does not have brush allodynia). The result for each side of forehead will be reported separately. The actual brush allodynia score will be summarized using the Full Analysis Population at each scheduled visit using descriptive statistics. The percent of subjects with brush allodynia (i.e. a score >0) will be summarized at each scheduled visit along with the percent of subjects with a score >2.

3.5 Pharmacokinetic Analyses

The concentrations of Free ALD403 will be measured in plasma from all ALD403-treated subjects using validated assay methods. The PK analysis will include evaluations of concentration-time profiles for Free ALD403 at the following times: pre-dose on Day 0, and Weeks 4, 8, 12, 16, 20, 24, 36, 48, and 56.

The concentrations of Free ALD403 will be listed and summarized by time point and dose group, and descriptive statistics will be provided. In this analysis, concentrations below the lower limit of quantification (LLOQ) will be set to zero.

Plots of the mean or median concentration will be presented over time (linear and log scales). When the scale is linear, concentrations below the lower limit of quantification will be set to zero. In the log-scaled figures, concentrations below the LLOQ will be imputed as LLOQ/2.

3.6 Analysis of Safety Endpoints

3.6.1 Adverse Events

Adverse events are collected from the time of Informed Consent through the final subject visit. The incidence of all AEs and treatment-related AEs will be tabulated by treatment received. These AEs will be classified by system organ class and preferred term using the MedDRA. For incidence reporting, if a subject reported more than 1 AE that was coded to the same preferred term/system organ class, the subject will be counted only once for that specific preferred term/system organ class. Events recorded between the time the informed consent is signed and the first Investigational Product administration will be listed.

A treatment-emergent AE (TEAE) is an AE with a start date on or after the date of the treatment.

For the purpose of inclusion in TEAE tables, incomplete AE onset and end dates will be imputed as follows:

Missing onset dates (where UK and UKN indicate unknown or missing day and month respectively):

- UK-MMM-YYYY: If the month and year are different from the month and year of the first dose of trial drug, assume 01-MMM-YYYY. If the month and year are the same as the first dose of trial drug month and year, and the end date (after any imputation) is on or after the first dose of trial drug, then assume the date of the first dose of trial drug. If the month and year are the same as the first dose of trial drug month, and year and the end date (after any imputation) is prior to the first dose of trial drug, then assume the end date for the onset date.
- DD-UKN-YYYY/UK-UKN-YYYY: If the year is different from the year of first dose of trial drug, assume 01-JAN-YYYY of the collected year. If the year is the same as the first

dose of trial drug year, and the end date (after any imputation) is on or after the first dose of trial drug, then assume the date of the first dose of trial drug. If the year is the same as the first dose of trial drug, and the end date (after any imputation) is prior to the first dose of trial drug, then assume the end date for the onset date.

Missing end dates (where UK and UKN indicate unknown or missing day and month respectively):

- UK-MMM-YYYY: Assume the last day of the month;
- DD-UKN-YYYY/UK-UKN-YYYY: Assume 31-DEC-YYYY.

An overview of AEs, which includes subject incidence of TEAEs, treatment-related TEAEs, Serious TEAEs, TEAEs leading to treatment withdrawal, TEAEs leading to treatment interruption, TEAEs leading to discontinuation and deaths will be presented.

The subject incidence of TEAEs and treatment-related TEAEs will be summarized by system organ class and preferred term.

Treatment-emergent AEs will also be summarized in a table by severity. For TEAEs presented by severity, the worst severity for each event during the clinical trial will be presented for each subject.

All AEs will be presented as a listing by subject. This listing will include the duration of the AE.

3.6.2 Deaths, Serious Adverse Events and Other Significant Adverse Events

3.6.2.1 Serious Adverse Events

All SAEs will be listed and summarized in a similar manner to TEAEs.

3.6.2.2 Deaths

A listing of deaths will be presented.

3.6.3 Clinical Laboratory Evaluations

Summary statistics for actual values and for changes from baseline will be tabulated for clinical laboratory results by scheduled visit. Subjects with clinical laboratory values outside of the normal reference range at any post-baseline assessment will be summarized. Shifts from baseline clinical laboratory values based upon the normal range and will be tabulated. Subjects developing an antibody response will be listed.

Additional blood specimens using the immune response lab kit will be collected for subjects who experience a potential systemic allergic reaction that the Investigator believes is related to ALD403.

Plots of average clinical laboratory parameters will be presented over time.

3.6.4 Vital Signs, Physical Findings and Other Observations Related to Safety

3.6.4.1 Vital Signs

The observed data at baseline and change from baseline for each measurement day will be summarized with descriptive statistics. A plot of average vital sign parameters will be presented over time.

3.6.4.2 Physical Exam

Clinically significant physical exam findings at screening will be documented in medical history. Post baseline physical examination findings, including unscheduled visits, will be reported as adverse events.

3.6.4.3 Electrocardiogram Results

The observed data at baseline and change from baseline for each measurement day will be summarized with descriptive statistics by treatment group.

The overall ECG assessment based upon PI assessment will be summarized including post treatment ECGs determined to be abnormal clinically significant.

35

The absolute QTcF values provided by the core lab will be analyzed as a categorical variable. Each QTcF value in a given patient will be grouped into 4 categories:

- QTcF interval < 450 msec
- QTcF interval 450 480 msec
- QTcF interval > 480 500 msec
- QTcF interval > 500 msec

The changes in QTcF measures will also be analyzed as categorical variables. The change in QTcF in a given patient will be grouped into 2 categories:

- QTcF interval increases from baseline > 30 msec
- QTcF interval increases from baseline > 60 msec

The overall ECG assessment will be summarized along with a summary of how many subject developed a post treatment abnormal clinically significant result. Denominators for percentages will use the number of assessments available at each visit.

